#### 6.5. Visit Windows

The time windows specified in Table 4.1 (Cohort 1 and 2) and Table 4.2 (Cohort 3) define how efficacy data will be assigned to protocol-specified time points. All time points and corresponding time windows are defined based on dosing date.

If more than one efficacy observation for a specific assessment is included in a time window, the assessment closer to the nominal time will be used. If there are two efficacy observations

equally distant to the nominal time, the latest one will be used in analyses. Any efficacy assessments occurring outside the analysis windows will be considered an assessment of an unscheduled visit.

**Table 4.1: Analysis Time Windows of Bayley Scales, HFMSE, Development Milestones and Pulmonary Exam – Cohort 1 and 2 Patients**

Scheduled Visit	Nominal Days (Study Day)	Acceptable Analysis Window in Study Days (Min Day – Max Day)
Baseline	-	< 1
Month 1	30	1 to 44
Month 2	60	45 to 74
Month 3	90	75 to 104
Month 4	120	105 to 134
Month 5	150	135 to 164
Month 6	180	165 to 194
Month 7	210	195 to 224
Month 8	240	225 to 254
Month 9	270	255 to 284
Month 10	300	285 to 314
Month 11	330	315 to 344
Month 12	360	≥345

**Table 4.2: Analysis Time Windows of Bayley Scales, HFMSE, Development Milestones and Pulmonary Exam – Cohort 3 Patients**

Scheduled Visit	Nominal Days (Study Day)	Acceptable Analysis Window in Study Days (Min Day – Max Day)
Baseline	-	< 1
Month 1	30	1 to 38
Day 44	44	39 to 49
Month 2	60	50 to 66
Day 72	72	67 to 77
Month 3	90	78 to 104
Month 4	120	105 to 134
Month 5	150	135 to 164
Month 6	180	165 to 194
Month 7	210	195 to 224
Month 8	240	225 to 254
Month 9	270	255 to 284
Month 10	300	285 to 314
Month 11	330	315 to 344
Month 12	360	345 to 374

Scheduled Visit	Nominal Days (Study Day)	Acceptable Analysis Window in Study Days (Min Day – Max Day)
Month 13	390	375 to 404
Month 14	420	405 to 434
Month 15	450	≥435

Safety data, such as laboratory results, vital signs, ECGs, and physical exams will be assessed by date and study day. For change from baseline analyses the value associated with the scheduled visit will be used. For summaries of shifts from baseline and potentially significant values all values will be considered for these analyses. Baseline for safety measures will be defined as the latest value before Day 1.

The efficacy data of this study will be compared to the data from the PNCR network. The analysis visit of PNCR will be based on the visit month defined in the PNCR dataset.

**Table 5: Analysis Time Windows for dataset from PNCR Network**

Scheduled Visit	PNCR
Baseline	Visit Month 0
Month 2	Visit Month 2
Month 4	Visit Month 4
Month 6	Visit Month 6
Month 9	Visit Month 9
Month 12	Visit Month 12

If a PNCR patient is missing efficacy data at Baseline, then the earliest non-missing assessment collected post-Baseline will be re-mapped and considered their Baseline value, and subsequent visits occurring within 12 months after the re-mapped Baseline value will be included in the analysis.

For example, if a PNCR patient is missing their HFMSE assessment at Visit Month 0 and Visit Month 2 and their first non-missing HFMSE assessment occurred at Month 4, then their data would be re-mapped as follows:

- Visit Month 4 assessment is considered Baseline
- Month 6 is re-mapped as Month 2 (visit occurred 2 months after Baseline)
- Month 9 is remapped as Month 5 (visit occurred 5 months after Baseline)
- Month 12 is remapped as Month 8 (visit occurred 8 months after Baseline)
- Next available visit is >12 months after Baseline so it is not considered

## 6.6. Pooling of Centers

This is a multiple-center dose-comparison study. Given that the number of patients enrolled at any individual site is expected to be small, patients from all sites will be pooled in the analyses for the primary and secondary effectiveness endpoints. A site effect or a site-treatment interaction will not be examined due to the fact that the sites selected for this study are all high-level treatment centers with extensive experience in the management of SMA and, as such, are

expected to follow care management strategies closely aligned with the published standards of care.

### **6.7. Subgroups**

There will be no subgroups created for the analysis.

### **6.8. Other Statistical Analysis**

Not applicable to this SAP.

Final

## 7. DEMOGRAPHIC, OTHER BASELINE CHARACTERISTICS AND MEDICATION

### 7.1. Patient Disposition and Withdrawals

Patient disposition will be presented for all patients, which will include the following:

- The number of patients screened
- The number of patients who failed screening
- The number (%) of patients in the Enrolled Set
- The number (%) of patients in the ITT Set
- The number (%) of patients in the FAS
- The number (%) of patients in the SS
- The number (%) of patients in the ECAS
- The number (%) of patients in the PP Set
- The number (%) of patients who completed the study, including all patients with a final scheduled visit conducted either remotely or at the study site
  - The number (%) of patients who completed the study within 30 days of when the last study visit was scheduled to occur
  - The number (%) of patients who completed the study more than 30 days after when the last study visit was scheduled to occur
    - For patients in dose groups A and B, the last study visit was scheduled to occur at Month 12 (Day 360) and 30 days after the last scheduled study visit is Day 390. For patients in dose group C, the last study visit was scheduled to occur at Month 15 (Day 450) and 30 days after the last scheduled study visit is Day 480.
- The number (%) of patients who discontinued from the study and the associated reasons

Patient disposition will be summarized overall and by dose and age group. A listing of patient disposition will be provided. The inclusion/exclusion criteria for the patients who failed screening and all major protocol deviations will be listed. A separate listing will be produced which summarizes all protocol deviations related to COVID-19.

A listing of patients excluded from the PP Set, along with reason for exclusion, will be provided.

For patients who discontinued due to AE, a separate summary table will be produced in order to detail the type of AE that resulted in the discontinuation (whether serious fatal, non-serious fatal, or non-fatal).

### 7.2. Demographic and Other Baseline Characteristics

Demographics and baseline characteristics will be summarized for the PNCR dataset and separately for the SS overall and by dose and age group, with descriptive statistics including n, mean, standard deviation, median, minimum, and maximum for numeric variables and frequency and percentage for categorical variables.

The following characteristics will be summarized for the SS:

Demographics include age, gender, ethnicity, race, weight, length and body mass index.

Age (months) = (dose date - date of birth +1)/30

Length (cm) = Length (in inches) \* 2.54

Weight (kg) = Weight (in lbs) \* 0.4536

Race will be summarized as captured in the eCRF. Patients reporting multiple races will be summarized as 'Multiple'.

Baseline disease characteristics include the following:

- Familial history of SMA including affected siblings or parent carriers
- Gestational age at birth
- Length/weight and head circumference at birth
- Hospitalization information from time of birth including number, duration, and reason for hospitalizations including primary ICD-10 codes if available
- Historical ventilatory support, if any
- Historical feeding support, if any

All demographics and baseline characteristics will be listed for the SS.

The following characteristics will be summarized for each of the three PNCR populations being referenced in this study (refer to Section 5.6 of this SAP):

- Age at PNCR entry (months)
- Age (months) at first HFMSE assessment conducted after reaching 24 months of age
- Gender
- Ethnicity
- Race
- Gestational age at birth
- Height (cm) at PNCR entry
- Weight (kg) at PNCR entry

### 7.3. Medical History and Concomitant Diseases

A summary table of the number and percentage of patients by medical history system organ class (SOC) and preferred term (PT) will be produced for patients in the ITT. The summary will be provided overall and by dose and age group. Medical history will be sorted alphabetically by SOC and PT using the Medical Dictionary for Regulatory Activities (MedDRA) coding dictionary. For the summary tables, a patient may appear more than once if he/she has more than one medical history coded under the same PT and/or SOC categories. However, the patient will be counted only once in each category.

A summary table of SMA medical history will be produced for patients in the ITT. The summary will be provided overall and by dose and age group.

Listings for medical history and SMA medical history will also be provided. Medical history and concomitant diseases data were not collected in a similar fashion in the PNCR natural history study and therefore the study data regarding medical history and concomitant disease will not be compared with the PNCR natural history cohort.

## 7.4. Medication

### 7.4.1. Prior and Concomitant Medications

All prior and concomitant medications will be classified using the Anatomical Therapeutic Chemical (ATC) classification and preferred drug names from the World Health Organization (WHO) Drug Dictionary, version March 2014 or later. Prior medications are defined as medications which started prior to injection of AVXS-101. Concomitant medications are defined as medications ongoing at time of first injection of AVXS-101 or started after the injection.

Prior and concomitant medications will be summarized separately by ATC level 2 and preferred drug name for the SS. The prior and concomitant medications will be summarized overall and by dose and age group.

A separate listing for prior and concomitant medications will also be provided. Prior and concomitant medication information is not available for the PNCR population matched cohort.

### 7.4.2. Specific Medication Subgroup

The total number of days receiving prednisolone and total cumulative dose of prednisolone administered during the entire study (mg/kg) will be computed for each patient. Only the data recorded on the prednisolone dosing log will be used in this derivation.

To compute total cumulative dose, the total dosing period is subdivided into dosing intervals represented by constant dose levels. On the day of a dosage change, the entire day is represented under the new dosing interval at the new dose.

For example, consider a patient who receives 1.0 mg/kg of prednisolone for Day 1 to Day 30, then on Day 31, dose is lowered to 0.5 mg/kg until Day 42. On Day 43, the dose is lowered to 0.25 mg/kg and continues until Day 56 when prednisolone dosing stops. For this patient,

$$\begin{aligned}\text{Total cumulative dose} = & (1.0 \text{ mg/kg} \times 30 \text{ days}) + \\ & (0.5 \text{ mg/kg} \times 12 \text{ days}) + \\ & (0.25 \text{ mg/kg} \times 14 \text{ days}) = 39.5 \text{ mg/kg}\end{aligned}$$

Exposure will be summarized overall and by actual dose received and age group for the SS.

A listing of AEs will be produced for patients who did not follow the protocol-defined taper, defined as those patients with less than 56 days of total time of prednisolone dosing.

### 7.4.3. Compliance to Study Product

Refer to Section 11.1 and Section 11.2 of this SAP.

#### 7.4.4. Measurement of Treatment Compliance

Refer to Section 11.1 and Section 11.2 of this SAP.

#### 7.4.5. Data Display Treatment and Other Sub-Group Description

Not applicable for this SAP.

#### 7.4.6. Other Therapies

Non-medication therapies/procedures will be defined as “prior” and/or “concomitant”. Prior non-medication therapies/procedures are defined as therapies or procedures started prior to injection of AVXS-101. Concomitant non-medication therapies/procedures are defined as therapies or procedures ongoing at time of injection of AVXS-101 or started after the injection.

Non-medication therapies/procedures will not be summarized in a table. Listings will be provided.

### 8. EFFICACY

#### 8.1. Primary Efficacy Endpoints and Analysis

##### 8.1.1. Proportion of patients $\geq$ 6 months and $<$ 24 months at time of dosing that achieve the ability to stand alone at any post-baseline visit up to 12 months

The developmental milestone stands alone as assessed by Bayley-III Gross Motor Subtest #40 will be assessed at the scheduled visits in accord with the Schedule of Assessments for evaluating patient’s ability to stand alone. The developmental milestone achievement of each patient in the study is based on the video evidence reviewed and confirmed by an independent central reviewer, as specified in SAP Section 6.4.3. The proportion of patients  $\geq$  6 months and  $<$  24 months of age at time of dosing that achieve the developmental milestone at any post-baseline visit up to 12 months will be summarized overall and by dose.

The proportion of patients achieving the corresponding developmental milestone “stand unsupported” assessed using the HFMSE item #19 within 12 months in the historical dataset of PNCR network will also be included by the matched age group. PNCR patients with an HFMSE item #19 score of 2 at either the Baseline visit or at any post-Baseline visit within 12 months of Baseline will be considered to have achieved the milestone. The HFMSE will not be started until patients reach 24 months of age; however, the Bayley-III will be assessed at Screening and all study visits as indicated in the Schedule of Assessments. An additional summary will be produced to present the proportion of patients achieving the developmental milestone at each visit; this will be summarized overall and by dose.

The corresponding p-value from Fisher’s exact test will be computed for the comparison between AVXS-101 Dose B and PNCR data and this is the primary analysis for this endpoint. The summary and statistical analysis will be conducted using the ITT Set and will be repeated using the PP Set as a sensitivity analysis. The difference of the proportions between AVXS-101 and PNCR will be summarized and the exact 95% CIs will be provided accordingly.

As a supporting analysis to the primary analysis, the time to achieving ability to stand alone will be summarized for patients overall and by dose in the ITT Set. The study day will be used as the

time variable. Age at baseline will be used as a covariate. The probability of the ability to stand alone over time will be estimated using Kaplan-Meier methods. A Cox regression model will be used to obtain the hazard ratio with 95% CI for AVXS-101 Dose B to the data from PNCR. In this analysis, patients will be censored at the date of their End of Study visit.

All of the efficacy analyses stated above may be repeated using the ECAS as a sensitivity analysis, in the event the ECAS contains a subset of patients of the ITT Set.

If necessary, an additional set of sensitivity analyses may be conducted to include patients who demonstrated the developmental milestone of standing alone (Bayley-III, Gross Motor Subtest #40) which occurred after but within 3 months of the upper bound of the Month 12 visit window (day 374) due to COVID-19 disruptions.

In the first sensitivity analysis, the proportion of patients  $\geq$  6 months and  $<$  24 months of age at time of dosing that achieve the developmental milestone at any post-baseline visit (considering the expanded 3-month window) will be summarized overall and by dose. The corresponding p-value from a Fisher's exact test will be computed for the comparison between AVXS-101 Dose B and PNCR data. The summary and statistical analysis will be conducted using the ITT Set. The difference in the proportions between AVXS-101 and PNCR will be summarized and the exact 95% CIs will be provided accordingly.

In the second sensitivity analysis, the time from dosing to achieving the ability to stand alone will be summarized for patients overall and by dose in the ITT Set. The study day will be used as the time variable. Age at baseline will be used as a covariate. The probability of the ability to stand alone over time will be estimated using Kaplan-Meier methods. A Cox regression model will be used to obtain the hazard ratio with 95% CI for AVXS-101 Dose B and PNCR. In this analysis, patients who demonstrated the developmental milestone within the expanded 3-month window after Month 12 will be censored at the last attended visit prior to when the Month 12 visit was scheduled to occur.

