The primary efficacy endpoint for the group of patients  $\geq$  6 months and  $<$  24 months of age at time of dosing will be the proportion of patients who achieve the ability to stand alone up to the 12-month study visit. Twenty-four (24) children aged  $\geq$  6 months and  $<$  24 months will be enrolled, with twelve (12) children receiving Dose B and twelve children receiving Dose C. The proportion of patients developing the ability to stand alone will be compared with a cohort of eligibility-matched patients from the PNCR natural history study of SMA; this comparison will be conducted for Dose B only. Based upon a review of eligibility-matched patients from the PNCR, fourteen percent (14%) of patients who meet the study criteria for patients  $\geq$  6 months and  $<$  24 months of age achieved the ability to stand alone, and ten percent (10%) achieved the ability to walk alone. It is expected that 85% of treated patients  $\geq$  6 months and  $<$  24 months of age will achieve the ability to stand alone and 60% will achieve the ability to walk alone. With this efficacy, a sample size of 12 patients would provide power of  $>$  90% to detect a significant difference compared with the matched control cohort with  $\alpha = 0.05$  using a two sample 2-sided Fisher exact test.

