## 5.6. PNCR Population-Matched Control Population

A population-matched control cohort will be drawn from the PNCR Natural History dataset. The PNCR is a large natural history study developed from a cohort of 337 patients with any form of spinal muscular atrophy followed at 3 large, internationally recognized tertiary medical centers with significant expertise in the management of SMA (Harvard University/Boston Children's Hospital, Columbia University and the University of Pennsylvania/Children's Hospital of Philadelphia).

Previously identified patients with any form of SMA, of any age, followed in PNCR site clinics and newly diagnosed patients were enrolled. All eligible patients were offered participation. Study visits were scheduled at baseline and at 2, 4, 6, 9, and 12 months and every 6 months thereafter. The SMA standard of care guidelines published in 2007 were used as a basis for providing uniform care among the study sites.

For purposes of this study, sitting (for SMA-II) was defined as being able to sit independently for > 10 seconds, and walking alone was defined as having scored 2 points on item #20 of the HFMSE at any time. All patients with SMA type 2 or 3 who provided sufficient records and follow-up for evaluation and met the basic entry criteria for the two cohorts of the AVXS-101-CL-102 study (3 copies of *SMN2*, symptom onset before 12 months of age and baseline and follow-up visits within the age criteria for the study) were considered for possible inclusion in the natural history comparison dataset. The *SMN2* modifier mutation (c.859G>C) described by Prior and colleagues (Prior et al., 2009) was not assessed in the PNCR study cohort.

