## 6. GENERAL ASPECTS FOR STATISTICAL ANALYSIS

### 6.1. General Methods

In general, descriptive statistical methods will be used to summarize the data from this study. Hypothesis testing will be performed for the efficacy endpoints based upon the predetermined sample sizes. Unless stated otherwise, the term “descriptive statistics” refers to number of patients (n), mean, median, standard deviation, minimum, and maximum for continuous data and frequencies and percentages for categorical data. Unless noted otherwise, the data will be sorted first by dose (Dose A, then Dose B, then Dose C), age group, patient number, and then by date within each patient number.

Unless noted otherwise, all safety tables will be summarized using the SS, by the actual dose received and by age group.

All descriptive statistics of efficacy tables will be summarized by the assigned dose and age group. The efficacy analyses will be performed to compare with the efficacy endpoints of patients assigned to AVXS-101 and patients drawn from a widely (peer-reviewed) published natural history dataset collected by the PNCR network; comparisons to the PNCR data will be conducted for Dose B only. Efficacy data for Dose A and Dose C will only be summarized descriptively and will not be compared to the PNCR data.

Efficacy analyses will be conducted on the ITT or ECAS as specified within each section, with analyses on the ECAS produced only if the ECAS contains a subset of patients of the ITT. Since the FAS and the ITT Set include the same patients (SAP Section 5.3), the ITT Set is used to represent the efficacy analyses by the FAS stated in the protocol.

Unless specified otherwise, all statistical testing and confidence intervals (CI) will be 2-sided and will be performed using an alpha level of 0.05. No adjustments for multiple comparisons will be made.

All statistical analyses will be conducted with the SAS® software package version 9.4 or higher.

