All efficacy analyses stated above may also be performed using the ECAS as a sensitivity analysis in the event the ECAS contains a subset of patients of the ITT Set. Additionally, a sensitivity analysis will be performed for patients aged  $\geq$  24 and  $<$  60 months at time of dosing using the Sensitivity PNCR group. This sensitivity analysis will be based on the ITT Set and separately using the ECAS in the event the ECAS contains a subset of patients of the ITT Set.

If necessary, an additional set of sensitivity analyses may be conducted to include patients in the  $\geq$  6 months and  $<$  24 months group who demonstrated the developmental milestone of walking alone which occurred after but within 3 months of the upper bound of the Month 12 visit window (day 374) due to COVID-19 disruptions.

In the first sensitivity analysis, the proportion of patients that achieve the developmental milestone at any post-baseline visit (considering the expanded 3-month window) will be summarized overall and by dose. The corresponding p-value from a Fisher's exact test will be

computed for the comparison between AVXS-101 Dose B and PNCR data. The summary and statistical analysis will be conducted using the ITT Set. The difference in the proportions between AVXS-101 and PNCR will be summarized and the exact 95% CIs will be provided accordingly.

In the second sensitivity analysis, the time from dosing to achieving the ability to walk alone will be summarized for patients overall and by dose in the ITT Set. The study day will be used as the time variable. Age at baseline will be used as a covariate. The probability of the ability to walk alone over time will be estimated using Kaplan-Meier methods. A Cox regression model will be used to obtain the hazard ratio with 95% CI for AVXS-101 Dose B and PNCR. In this analysis, patients who demonstrated the milestone within the expanded 3-month window after Month 12 will be censored at the last attended visit prior to when the Month 12 visit was scheduled to occur.

Final

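### The optional COVID-19 Fisher analyses of standing and walking lengthen the success window for delayed Dose B children but not for PNCR controls, so they can shift only towards AVXS-101, though by little

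*SAP*

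**What the plan says.** **Treated children.** SAP 8.1.1 provides, if necessary, for an extra set of analyses that includes children who stood alone after day 374 but within 3 months of it because of COVID-19 disruption. In the first of these, the proportion who achieve the milestone "at any post-baseline visit (considering the expanded 3-month window) will be summarized overall and by dose". A "p-value from a Fisher's exact test will be computed for the comparison between AVXS-101 Dose B and PNCR data", and the difference in proportions gets an exact 95% CI. SAP 8.2.1 repeats this for walking in the same age group, again "at any post-baseline visit (considering the expanded 3-month window) will be" summarized and tested.

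**Controls.** For standing, SAP 8.1.1 says that PNCR patients with a score of 2 on HFMSE item 19 "at either the Baseline visit or at any post-Baseline visit within 12 months of Baseline will be considered to have achieved the milestone". SAP 8.2.1 has the matching rule for walking (item 20). Neither COVID-19 paragraph changes these rules. Table 5 in SAP 6.5 ends at Month 12, and the remapping example below it drops visits more than 12 months after Baseline. On PNCR follow-up, SAP 5.6 says: "Study visits were scheduled at baseline and at 2, 4, 6, 9, and 12 months and every 6 months thereafter".

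**Companion analysis.** The second COVID-19 analysis (Kaplan-Meier and Cox) censors the same late achievers at the last visit attended before Month 12 was due.

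**Day 374.** In SAP 6.5 this is the upper limit of Month 12 only in Table 4.2, which covers Cohort 3. Table 4.1, which covers Dose B, sets Month 12 at day 345 or later with no upper limit.

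**The concern.** Standing and walking are skills that some of these children gain with time. SAP 3.7 expects a small share of eligible children eventually to walk in the ordinary course of the disease. If delayed treated children get roughly 3 more months and controls do not, the change can add treated successes but never control successes. The estimated difference can then only rise, and part of the rise would be read as a drug effect. A check meant to show that the result survives delayed visits would instead be tilted one way, with a p-value and CI printed beside the primary result.

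**Working it through.** **Inputs.** There are 12 Dose B children, with expected rates of 85% standing and 60% walking (SAP 3.7). PNCR has 51 controls, of whom 7 stood and 5 walked (SAP 5.6.1). Under SAP 6.1, tests "will be 2-sided and will be performed using an alpha level of 0.05".

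**Step 1: the plan's own figure.** Exact power = Σx Σy Bin(x; 12, pT) · Bin(y; 51, pC) · 1[Fisher p ≤ 0.05].
- Standing, 0.85 vs 7/51: 0.999.
- Walking, 0.60 vs 5/51: 0.945.

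The stated power above 90% reproduces for both.

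**Step 2: the windows.** With 30-day months, 374 + 3 × 30 = day 464. Relative to 12 months, 464/360 = 1.29, or 464/365 = 1.27.

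**Step 3: natural rate by day 464.** Assume that 7/51 and 5/51 are 12-month rates and that the hazard is constant. The extended rate is p_ext = 1 − (1 − pC)^(464/D), where D is the length of 12 months in days (360 or 365).
- Standing: from 13.7% to 17.3% (D = 360) or 17.1% (D = 365).
- Walking: from 9.8% to 12.5% or 12.3%.

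**Step 4: false significance favouring AVXS-101 with no drug effect.** With k late children, treated successes are Bin(k, p_ext) + Bin(12 − k, pC), and controls are Bin(51, pC). Sum over tables with Fisher p ≤ 0.05 and the treated rate above the control rate:

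| Late children k | Standing, D = 360 | Standing, D = 365 |
|---|---|---|
| 0 | 2.25% | 2.25% |
| 1 | 2.4% | 2.4% |
| 2 | 2.6% | 2.6% |
| 3 | 2.8% | 2.7% |
| 4 | 2.9% | 2.9% |
| 12 | 4.8% | 4.6% |

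Walking runs from 2.25% (k = 0) to 4.3% (D = 360) or 4.2% (D = 365) at k = 12. If both groups are extended equally with D = 360, the figures are 2.2% for standing and 2.3% for walking.

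**Step 5: single results.**
- 4/12 vs 7/51: p = 0.197.
- 5/12 vs 7/51: p = 0.041.
- 5/12 vs 8/51: p = 0.105.

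Near the boundary, one late success on either side decides the test. At the planned effect (0.85 × 12 ≈ 10), 10/12 vs 7/51 gives p ≈ 0.00001, and even 10/12 vs 10/51 gives p ≈ 0.00007.

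**Step 6: a Month 18 control window.** Month 18 is day 540 (18 × 30) to about day 548 (18 × 365/12). Then 540/464 = 1.16 and 548/464 = 1.18, so the control window would be 16–18% longer than the treated one.

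**The case against.** The other side has a good deal to stand on.

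- **Scope.** The analysis is optional, limited to COVID-19 delays in the younger group, and does not replace the primary test. The figure with all 12 late is a ceiling, and the documents do not say how many visits were late. This stands.
- **The companion analysis.** A reader might infer that the whole COVID-19 set is tilted. It is not: the Cox analysis does not count late achievers as events, so it does not share this bias.
- **Late detection.** Protocol 11.2 and 11.3 date a milestone by when it is observed or shown on video. Some late dates will therefore reflect late detection, whereas the hazard model treats all the extra time as new development. This makes the computed effect, if anything, too large.
- **The control count.** SAP 5.6.1 gives 7/51 and 5/51 with no time limit, and the SAP 5.0 change summary speaks of milestones reached at any point. If those counts were used unchanged, the control window would not necessarily be shorter. Crediting controls for milestones already present at Baseline also works against AVXS-101. A reader might infer that the overall PNCR comparison is biased towards the drug, but the documents do not settle that.
- **Table 4.1.** Because its Month 12 window is open-ended for Dose B, the primary test may already count late treated milestones. This does not remove the concern. It means the asymmetry may not be confined to the sensitivity analysis.

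What remains is that the operative rules in 8.1.1 and 8.2.1 say 12 months for controls, and nothing in the COVID-19 paragraphs extends them.

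**Conclusion.** The concern holds in a limited form. As written, the COVID-19 Fisher analyses give delayed Dose B children until about day 464 and PNCR controls 12 months, so the result can shift only in AVXS-101's favour. For standing, the chance of a false significant result favouring the drug rises from about 2.3% to 2.4–2.9% with one to four late children, and to at most 4.6–4.8% with all 12 late. These figures assume that 7/51 is a 12-month rate, that the hazard is constant and that the drug has no effect.

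A reader might infer that false positives are seriously inflated or that the primary finding is undermined. The figures do not support that: even the ceiling is below 5%, and at an 85% response the conclusion is unchanged. The practical loss is that this p-value and CI cannot serve as independent support for a borderline primary result.

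**What to change.** 1. In 8.1.1 and 8.2.1, report the extended treated proportion descriptively, with no Fisher p-value or CI against PNCR. This costs only wording.
2. Alternatively, keep the test but count PNCR milestones through Month 18 where those data exist, and state that the control window is then about 16–18% longer than the treated one and so conservative. This costs one more PNCR visit in the derivation and a check of availability: SAP 5.6 shows that later visits were scheduled, not that data exist for these 51 children. PNCR has no scheduled visit between Months 12 and 18, so an exactly equal window may add few control observations.
3. Give the Dose B Month 12 window in Table 4.1 the day-374 upper bound that 8.1.1 and 8.2.1 assume, so that the primary analysis does not already count late treated milestones.
4. State in 5.6.1 whether 7/51 and 5/51 are within-12-month or any-time counts.

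Items 3 and 4 need SAP wording, a rerun of the visit-window derivation and, if the counts prove to be any-time, a recount of control successes under the 12-month rule.
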